Pregnancy Test (WOCBP only)	X	Serum or urine pregnancy test to be done within 24 hours prior to first dose, and then every 4 weeks (± 1 week) regardless of dosing schedule
Efficacy Assessments		
Tumor Imaging Assessment		See separate Table 5.1-14

Table 5.1-10: Re-initiation Procedural Outline (Nivolumab Ipilimumab Combination, CA209142): MSI-H (Arm N+I, cStage 1/2)

Procedure	See Section 4.3.1 for Re-initiation Treatment Schedule and Duration To Be Performed at Each Dosing Visit	Notes Visit Window : ± 2 Days
Exploratory Biomarker Testing		
Soluble Biomarkers (Serum)		See separate Table 5.6.8-5
Peripheral Blood Mononuclear Cells (PBMCs) Immuno- phenotyping		See separate Table 5.6.8-5
Ex vivo Functional assay (PBMCs)		See separate Table 5.6.8-5
Tumor tissue sample (biopsy) (optional)		See separate Table 5.6.8-5
Whole blood gene expression		See separate Table 5.6.8-5
Plasma Sample		See separate Table 5.6.8-5
SNP (whole blood)	See separate Table 5.6.8-5	
Clinical Drug Supplies		
IVRS Drug Vial Assignment	X	Vials may be assigned up to 2 days prior to first dose date.
Dispense Study Drug	X	Within 3 days from vial allocation, the subject must receive the first dose of study medication. Following first nivolumab dose, subsequent nivolumab dosing will be based on the actual date of administration of the previous dosing. Subjects may be dosed within a ± 3-day window of scheduled dose due to scheduling conflict. Subjects may be dosed no less than 19 days between doses for the first 4 doses of nivolumab and ipilimumab. For the remaining doses, subjects may be dosed no less than 25 days between doses of nivolumab.

Table 5.1-11: Re-initiation Schedule for C3 Cohort [Nivolumab 360 mg Q3W + Ipilimumab 1 mg/kg Q6W] No Prior **Treatments in Metastatic Setting** Notes To Be Performed at Each Dosing Visit, **Visit Window: ± 2 Days Unless Otherwise Specified in Notes or Procedure** See Section 4.3.1 for Re-initiation Treatment Schedule and Separate Table Duration **Safety Assessments** Targeted examination must include at a minimum the following body systems: Cardiovascular X **Targeted Physical Examination** Gastrointestinal Pulmonary Neurological exam for subjects with brain metastases Including BP, HR, temperature. Obtain vital signs within 72 hours prior Vital Signs X to first dose. Weight and ECOG performance status. Physical Measurements (including X performance status) See Appendix 2 for ECOG Performance Status scale. Review of Concomitant X Medication Adverse Events Assessment Χ On-study local laboratory assessments (after first dose) should be done within 72 hours prior to each dose through Week 23 and every dose thereafter and include: Χ CBC w/differential and platelet count, **Laboratory Tests** LFTs (ALT, AST, total bilirubin, alkaline phosphatase), BUN or serum urea level, creatinine, Ca, Mg, Na, K, Cl, LDH, glucose, amylase, lipase, TSH with reflexive Free T4, Free T3. Serum or urine pregnancy test to be done within 24 hours prior to first Pregnancy Test (WOCBP only) X dose, and then every 4 weeks (± 1 week) regardless of dosing schedule

Table 5.1-11: Re-initiation Schedule for C3 Cohort [Nivolumab 360 mg Q3W + Ipilimumab 1 mg/kg Q6W] No Prio Treatments in Metastatic Setting			
Procedure	To Be Performed at Each Dosing Visit, Unless Otherwise Specified in Notes or Separate Table	Notes Visit Window: ± 2 Days See Section 4.3.1 for Re-initiation Treatment Schedule and Duration	
Efficacy Assessments			
Tumor Imaging Assessment		See separate Table 5.1-14	
Exploratory Biomarker Testing			
Soluble Biomarkers (Serum)		See separate Table 5.6.8-5	
Peripheral Blood Mononuclear Cells (PBMCs) Immuno- phenotyping	See separate Table 5.6.8-5		
Ex vivo Functional assay (PBMCs)	See separate Table 5.6.8-5		
Tumor tissue sample (biopsy) (optional)	See separate Table 5.6.8-5		
Whole blood gene expression	See separate Table 5.6.8-5		
Plasma Sample	See separate Table 5.6.8-5		
SNP (whole blood)	See separate Table 5.6.8-5		
Clinical Drug Supplies			
IVRS Drug Vial Assignment	X	Vials may be assigned up to 2 days prior to first dose date.	
Dispense Study Drug	X	Within 3 days from treatment assignment, the subject must receive the first dose of study medication. Subjects may be dosed no less than 19 days between nivolumab doses, and no less than 5 weeks between ipilimumab doses.	

Table 5.1-12: Re-initiation for C5 Cohort (Nivolumab: MSI-H Nivolumab 240 mg Q2W + BMS-986016 [LAG3] 160 mg Q2W)

Procedure	To Be Performed at Each Dosing Visit, Unless Otherwise Specified in Notes or Separate Table	Notes Visit Window: ± 2 Days See Section 4.3.1 for Re-initiation Treatment Schedule and Duration
Safety Assessments		
Targeted Physical Examination	X	Targeted examination must include at a minimum the following body systems: Cardiovascular Gastrointestinal Pulmonary Neurological exam for subjects with brain metastases
Neurological Exam	X	Obtain neurological exam (performed by a neurologist) in subjects who experience a study drug related ≥ Grade 2 neurological AE.
Vital Signs	X	Including BP, HR, temperature. Obtain vital signs within 72 hours prior to first dose
Physical Measurements (including performance status)	X	Weight and ECOG performance status. See Appendix 2 for ECOG Performance Status scale.
12-lead electrocardiogram (ECG)	X	12-lead ECG to be performed within 72 hours prior to dosing
Review of Concomitant Medication	X	
Adverse Events Assessment	X	

Table 5.1-12: Re-initiation for C5 Cohort (Nivolumab: MSI-H Nivolumab 240 mg Q2W + BMS-986016 [LAG3] 160 mg Q2W)

Procedure	To Be Performed at Each Dosing Visit, Unless Otherwise Specified in Notes or Separate Table	Notes Visit Window: ± 2 Days See Section 4.3.1 for Re-initiation Treatment Schedule and Duration	
		On-study local laboratory assessments (after first dose) should be done within 72 hours prior to each dose through Week 23 and every alternate dose thereafter and include:	
		CBC w/differential and platelet count,	
Laboratory Tests	X	LFTs (ALT, AST, total bilirubin, alkaline phosphatase), BUN or serum urea level, creatinine, Ca, Mg, Na, K, Cl, LDH, glucose, amylase, lipase, TSH with reflexive Free T4, Free T3.	
		Performed for the C5 Cohort Only: Cardiac Troponin Levels: T (cTnt) or I (cTnI). Labs are performed locally, and may be collected within 72 hours prior to dosing. Results must be reviewed by the Investigator or appropriate designee prior to dose administration.	
Pregnancy Test (WOCBP only)	X	Serum or urine pregnancy test to be done within 24 hours prior to first dose, and then every 4 weeks (± 1 week) regardless of dosing schedule	
Efficacy Assessments			
Tumor Imaging Assessment		See separate Table 5.1-14	
Exploratory Biomarker Testing			
Soluble Biomarkers (Serum)		See separate Table 5.6.8-6	
Peripheral Blood Mononuclear Cells (PBMCs) Immuno- phenotyping		See separate Table 5.6.8-6	
Ex vivo Functional assay (PBMCs)	See separate Table 5.6.8-6		
Tumor tissue sample (biopsy) (optional)		See separate Table 5.6.8-6	
Whole blood gene expression		See separate Table 5.6.8-6	

Table 5.1-12: Re-initiation for C5 Cohort (Nivolumab: MSI-H Nivolumab 240 mg Q2W + BMS-986016 [LAG3] 160 mg Q2W)

Procedure	To Be Performed at Each Dosing Visit, Unless Otherwise Specified in Notes or Separate Table	Notes Visit Window: ± 2 Days See Section 4.3.1 for Re-initiation Treatment Schedule and Duration		
Plasma Sample	See separate Table 5.6.8-6			
SNP (whole blood)	See separate Table 5.6.8-6			
Clinical Drug Supplies				
IVRS Drug Vial Assignment	X Vials may be assigned up to 2 days prior to first dose			
Dispense Study Drug	X	Within 3 days from treatment assignment, the subject must receive the first dose of study medication.		

Protocol Amendment No: 09 Date: 27-Aug-2021

Approved v1000 930073805 10.0

Procedure	Re-initiation (R) Follow Up, Visits 1(R) and 2(R) ^a	Survival Follow-Up Visits ^b	Notes
Safety Assessments			
Targeted Physical Examination	X		To assess for potential late emergent study drug related issues Targeted examination must include at a minimum the following body systems: • Cardiovascular • Gastrointestinal
			PulmonaryNeurological exam for subjects with brain metastases
Adverse Events Assessment	X		In Survival Follow-Up period only to include toxicities from study therapy
ECG	X		Only at FU1(R)
Review of Concomitant Medication	X	X	Subsequent Cancer Therapy
Laboratory Tests	X		CBC w/ differential and platelet count, LFTs, BUN or serum urea level, creatinine, Ca, Mg, Na, K, Cl, LDH, Glucose, amylase, lipase, TSH (+ reflex Free T4 and Free T3) To be done at FU1(R). To be repeated at FU2(R) if study related toxicity persists.
Troponin	X	X*	Performed for the C5 Cohort Only. All results should be checked as soon as possible. *Troponin testing as clinically indicated, at the discretion of the treating physician during survival follow-up.
Pregnancy Test (WOCBP only)	X		Serum or urine
Efficacy Assessments			
Tumor Imaging Assessment	See note	See note	See separate Table 5.1-14

Table 5.1-13: Follow-Up (Discontinuation of Re-initiated Treatment, CA209142)					
Procedure	Notes				
Subject Status					
Survival Status		X	Every 3 months after F-U 2 (R); may be accomplished by visit, phone contact or email, to assess subsequent anti-cancer therapy for a minimum of 5 years, in all cohorts. (Please see Section 3.1.10 for end of the study definition.)		

Subjects must be followed for at least 100 days after last dose of study therapy. Follow-up visit #1 after re-initiation (FU1 R) occurs approximately 35 days (± 7 days) after last dose or coinciding with the date of discontinuation (± 7 days) if date of discontinuation is greater than 35 days after last dose. Follow up after re-initiation visit #2 (FU2 R) occurs approximately 80 days (± 7 days) after FU1 (R).

Table 5.1-14a: Standard Tumor Imaging Assessment

Tumor imaging assessments will occur every 6 weeks from the date of first dose (\pm 1 week) for the first 24 weeks, then every 12 weeks (\pm 1 week) thereafter until disease progression or treatment is discontinued (whichever occurs later).

Table 5.1-14b: Reduced Tumor Imaging Assessment

All Subjects (Except Re-initiation Subjects)	Re-initiation Subjects
Scans every 12 weeks (\pm 1 week) for 3 years after first dose, then every 24 weeks (\pm 2 weeks) thereafter*	Scans every 12 weeks (\pm 1 week) for 3 years after first dose following reinitiation, then every 24 weeks (\pm 2 weeks) thereafter ^a

 $^{^{\}mathrm{a}}$ Scans may continue every 12 weeks (\pm 1 week) if clinically indicated.

Notes: CT or MRI chest, abdomen, pelvis and all known sites of disease. Use same imaging method as was used at screening/baseline.

Subjects with a history of brain metastasis may have surveillance MRI approximately every 12 weeks from the date of first dose, or sooner if clinically indicated.

Protocol Amendment No: 09

b Survival visits = every 3 months from FU2 (R). Survival visits will be conducted for all MSI-H subjects who have re-initiated treatment.

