viii) Cardiac Troponin T (cTnT) or I (cTnI) $\leq 2 \times$ institutional ULN. Subjects with cTnT or cTnI levels between ≥ 1 to $2 \times$ ULN will be permitted if repeat levels within 24 hours are ≤ 1 ULN (**Cohort C5 only**)

- (1) If cTnT or cTnI levels are >1 ULN at 24 hours, the subject may undergo a cardiac evaluation and be considered for treatment, following a discussion with the BMS Medical Monitor or designee.
- j) Re-enrollment: This study permits the re-enrollment of a subject that has discontinued the study as a pre-treatment failure (ie, subject has not been treated / has not been treated). If re-enrolled, the subject must be re-consented.
- k) LVEF assessment with documented LVEF \geq 50% by either TTE or MUGA (TTE preferred test) within 6 months from first study drug administration (**Cohort C5 only**)

3) Age and Reproductive Status

- a) Men and women, ages ≥ 18 years of age
- b) Women of childbearing potential (WOCBP) must have a negative serum or urine pregnancy test (minimum sensitivity 25 IU/L or equivalent units of HCG) within 24 hours prior to the start of study drug.
- c) Women must not be breastfeeding
- d) WOCBP must agree to follow instructions for method(s) of contraception from the time of enrollment for the duration of treatment with study drug(s) plus time required for the investigational drug to undergo approximately five half-lives plus 30 days (duration of ovulatory cycle) for a total of 5 months post treatment completion.
- e) Men who are sexually active with WOCBP must agree to follow instructions for method(s) of contraception for the duration of treatment with study drug(s) plus time required for the investigational drug to undergo approximately five half-lives plus 90 days (duration of sperm turnover) for a total of 7 months post-treatment completion.
- f) Azoospermic males and WOCBP who are continuously not heterosexually active are exempt from contraceptive requirements. However, WOCBP must still undergo pregnancy testing as described in these sections.
- g) During the study and for 3 months after receiving the last dose of daratumumab, a woman must agree not to donate eggs (ova, oocytes) for the purposes of assisted reproduction.

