Note: See for Section 3.1.4.1 for treatment duration

Nivolumab and Ipilimumab combination:

When both nivolumab and ipilimumab are to be administered on the same day, separate infusion bags and filters must be used for each infusion. Nivolumab is to be administered first. The nivolumab infusion must be promptly followed by a saline flush to clear the line of nivolumab before starting the ipilimumab infusion. The second infusion will always be ipilimumab and will start no sooner than 30 minutes after completion of the nivolumab infusion.

Dosing calculation based on weight:

The dosing calculations should be based on the body weight. If the subject's weight on the day of dosing differs by > 10% from the weight used to calculate the dose, the dose must be recalculated. The weight used to calculate the dose should always be the most recently recorded weight. All doses should be rounded to the nearest milligram. There will be no dose modifications allowed.

Body weight is determined as detailed in the Flow Chart/Time and Events Schedule of this protocol.

Dosing modifications:

There will be no dose modifications allowed for the management of toxicities of individual subjects.

For Q2W nivolumab dosing cycles, subjects may be dosed no less than 12 days between doses. For Q3W nivolumab dosing cycles, subjects may be dosed no less than 19 days between doses. For Q4W nivolumab dosing cycles, participants may be dosed no less than 25 days from the previous dose. For Q6W ipilimumab dosing cycles, participants may be dosed no less than 5 weeks from the previous dose. If dosing is delayed, both nivolumab and ipilimumab must be delayed together. If dosing is resumed after a delay, both nivolumab and ipilimumab must be resumed on the same day.

Table 4.3-5: Dosing Schedule for C5 Cohort: Nivolumab + BMS-986016 Combination		
Day 1 Week 1	Day 1, Week 3, 5, 7, 9 and every other week thereafter*	
240 mg nivolumab flat dose	240 mg nivolumab flat dose IV over 30 minutes	
160 mg BMS-986016	160 mg BMS986016 IV over 60 minutes	

Note: See for Section 3.1.4.1 for treatment duration

Table 4.3-6: Dosing Schedule for C6 Cohort: Nivolumab + Daratumumab Combination				
Drug	Dose	Frequency of administration	Route of administration	Duration
Nivolumab	240 mg flat dose	every 2 weeks starting on Week3	30 minute Intravenous (IV) infusion	Until progression, toxicity, or discontinuation from study

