4.3.3 Dose Delay Criteria

Dose delay criteria apply for all drug-related adverse events (regardless of whether or not the event is attributed to nivolumab, ipilimumab, BMS-986016, daratumumab, or combinations). All study drugs must be delayed until treatment can resume (see Section 4.3.5). Treatment delays up to 6 weeks from the last dose are allowable. Study therapy should also be delayed in cases of confirmed or suspected severe acute respiratory syndrome coronavirus 2 (SARS-CoV-2) infection, regardless of the severity.

Nivolumab and ipilimumab administration should be delayed for the following:

- Any Grade ≥ 2 non-skin, drug-related adverse event, with the following exceptions:
 - Grade 2 drug-related fatigue or laboratory abnormalities do not require a treatment delay
- Any Grade 3 skin, drug-related adverse event
- Any Grade 3 drug-related laboratory abnormality, with the following exceptions for asymptomatic amylase or lipase, AST, ALT, or total bilirubin:
 - Grade 3 amylase or lipase abnormalities that are not associated with symptoms or clinical manifestations of pancreatitis do not require a dose delay.
 - If a subject has a baseline AST, ALT, or total bilirubin that is within normal limits, delay dosing for drug-related Grade ≥ 2 toxicity
 - If a subject has baseline AST, ALT, or total bilirubin within the Grade 1 toxicity range, delay dosing for drug-related Grade ≥ 3 toxicity

Nivolumab and BMS-986016 (C5 Cohort treatment) administration should be delayed for the following:

- Select drug-related AEs and drug-related laboratory abnormalities:
 - ≥ Grade 3 skin
 - ≥ Grade 1 pneumonitis
 - \geq Single grade increase shift in abnormality in AST, ALT, and total bilirubin
 - ≥ Grade 2 creatinine
 - ≥ Grade 2 diarrhea or colitis

- ≥ Grade 2 neurological AE
- Grade 4 amylase and/or lipase abnormalities regardless of symptoms or clinical manifestations
- ≥ 1x ULN troponin, hold dose and repeat troponin after 24 hours. All troponin elevations require a dose delay to allow for prompt cardiac evaluation. Following this evaluation, determination of further treatment will be based on the discretion of the PI.
- Any AE, laboratory abnormality, or concurrent illness that, in the judgment of the Investigator, warrants delaying the dose of study drug
- Grade 2 Myocarditis

Nivolumab and daratumumab (C6 Cohort treatment) administration should be delayed for the following:

- Grade 4 hematologic toxicity, except for Grade 4 lymphopenia

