4.3.5 Criteria to Resume Treatment

Subjects may resume treatment with study drug when the drug-related AE(s) resolve to Grade ≤ 1 or baseline value, with the following exceptions:

- Subjects may resume treatment in the presence of Grade 2 fatigue
- Subjects who have not experienced a Grade 3 drug-related skin AE may resume treatment in the presence of Grade 2 skin toxicity
- Subjects with baseline Grade 1 AST/ALT or total bilirubin who require dose delays for reasons other than a 2-grade shift in AST/ALT or total bilirubin may resume treatment in the presence of Grade 2 AST/ALT OR total bilirubin. Subjects with combined Grade 2 AST/ALT AND total bilirubin values meeting discontinuation parameters (Section 4.3.6) should have treatment permanently discontinued
- Drug-related pulmonary toxicity, diarrhea, or colitis, must have resolved to baseline before treatment is resumed
- Drug-related endocrinopathies adequately controlled with only physiologic hormone replacement may resume treatment
- Subjects in the C5 Cohort may resume treatment with BMS-986016 when troponin levels return to normal

In the case of prior SARS-CoV-2 infection, symptoms should have resolved in order to resume study treatment and there should be no sequelae that would place the participant at a higher risk of receiving study intervention.

If the criteria to resume treatment are met, the subject should restart treatment at the next scheduled time point per protocol. However, if the treatment is delayed past the scheduled time point per protocol, the scheduled study treatment administration will be delayed, but not skipped, until

dosing resumes. In particular, this is to ensure that subjects in Arm N+I will receive 4 administrations of combined nivolumab and ipilimumab treatment if toxicity allows.

If dose delay is necessary for subjects in Arm N+I during Week 1-12 and for subjects in Cohort C3, both nivolumab and ipilimumab must be delayed until treatment can resume. However, if a nivolumab-related infusion reaction prevents subsequent infusion of ipilimumab on the same day, the dose of ipilimumab should be replaced as soon as possible. In such instances, at least 19 days must elapse between the replacement dose of ipilimumab and the administration of the next dose of nivolumab combined with ipilimumab.

If treatment is delayed > 6 weeks from the last dose, the subject must be permanently discontinued from study therapy, except as specified in Section 4.3.6.

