		The dosing calculations should be based on the body weight. All doses should be rounded to the nearest milligram.	

Table 5.1-5: Short-term Procedural Outline for C5 Cohort [Nivolumab + Anti-Lag-3 (BMS-986016)]: MSI-H

Procedure	To Be Performed at Each Dosing Visit, Unless Otherwise Specified in Notes or Separate Table	Notes Visit Window: ± 2 Days See Section 3.1.4.1 for treatment duration
Safety Assessments		
Targeted Physical Examination	X	Targeted examination must include at a minimum the following body systems: Cardiovascular Gastrointestinal Pulmonary Neurological exam for subjects with brain metastases
Neurological Exam	X	Obtain neurological exam (performed by a neurologist) in subjects who experience a study drug related ≥ Grade 2 neurological AE.
Vital Signs	X	Including BP, HR, temperature. Obtain vital signs within 72 hours prior to first dose
Physical Measurements (including performance status)	X	Weight and ECOG performance status. See Appendix 2 for ECOG Performance Status scale.
12-lead electrocardiogram (ECG)	X	12-lead ECG to be performed within 72 hours prior to dosing
Review of Concomitant Medication	X	
Adverse Events Assessment	X	

Table 5.1-5: Short-term Procedural Outline for C5 Cohort [Nivolumab + Anti-Lag-3 (BMS-986016)]: MSI-H

Procedure	To Be Performed at Each Dosing Visit, Unless Otherwise Specified in Notes or Separate Table	Notes Visit Window: ± 2 Days See Section 3.1.4.1 for treatment duration
		On-study local laboratory assessments (after first dose) should be done within 72 hours prior to each dose through Week 23 and every alternate dose thereafter and include:
Laboratory Torte	V	CBC w/differential and platelet count, LFTs (ALT, AST, total bilirubin, alkaline phosphatase), BUN or serum
Laboratory Tests	X	urea level, creatinine, Ca, Mg, Na, K, Cl, LDH, glucose, amylase, lipase, TSH with reflexive Free T4, Free T3.
		Performed for the C5 Cohort Only: Cardiac Troponin Levels: T (cTnt) or I (cTnI). Labs are performed locally, and may be collected within 72 hours prior to dosing. Results must be reviewed by the Investigator or appropriate designee prior to dose administration.
Pregnancy Test (WOCBP only)	X	Serum or urine pregnancy test to be done within 24 hours prior to first dose, and then every 4 weeks (± 1 week) regardless of dosing schedule
Efficacy Assessments		
Tumor Imaging Assessment		See separate Table 5.1-14
Outcomes Research Assessment		

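### Cohort C5: the conditions for further treatment when troponin stays raised differ between Sections 4.3.3 and 4.3.5, and the troponin schedule after Week 23 can be read two ways

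*Combined protocol and SAP*

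**What the plan says.** **After a raised value.** Section 4.3.3 opens by requiring every study drug to be delayed until treatment can resume, and refers to Section 4.3.5 for that. For C5 it delays nivolumab and BMS-986016 at a troponin of 1x ULN or more, calls for a repeat after 24 hours and a cardiac evaluation, and then says: "Following this evaluation, determination of further treatment will be based on the discretion of the PI". Section 4.3.5 has a general rule (resolution to Grade 1 or less, or to baseline) followed by a list of exceptions. One of these is: "Subjects in the C5 Cohort may resume treatment with BMS-986016 when troponin levels return to normal".

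**At entry.** Inclusion criterion 2(i)viii in Section 3.3.1 admits C5 subjects with troponin up to 2x ULN if a repeat within 24 hours is no higher than 1x ULN. If the repeat is still above 1x ULN, sub-item (1) says "the subject may undergo a cardiac evaluation and be considered for treatment, following a discussion with the BMS Medical Monitor or designee". Section 4.3.9, item 4, applies criterion 2i again at re-initiation.

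**Timing.** The Laboratory Tests row of Table 5.1-5 says local tests "should be done within 72 hours prior to each dose through Week 23 and every alternate dose thereafter and include" a panel of blood tests. A separate paragraph in the same cell, marked as for C5 only, adds troponin, allows collection within 72 hours before dosing, and says: "Results must be reviewed by the Investigator or appropriate designee prior to dose administration". The column heading is "To Be Performed at Each Dosing Visit, Unless Otherwise Specified in Notes or Separate Table". Section 3.1.4.6 counts troponin among the on-study laboratory assessments and refers to Table 5.1-5 for the schedule. Table 5.1-12, for C5 re-initiation, repeats both the laboratory frequency ("prior to each dose through Week 23 and every alternate dose thereafter and include") and the review-before-dose sentence. The 12-lead ECG row in both tables carries no relaxation after Week 23.

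**The concern.** Section 1.5 lists troponin testing as one of six cardiovascular measures added for C5 after a Grade 4 ventricular fibrillation and a Grade 4 myocarditis with this combination. Section 1.4.3.3 reports that the myocarditis later became Grade 5. A safeguard adopted for that reason should tell a site when the test is due and what must be true before the next dose.

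As written, two sites holding the same raised result could act differently and both cite the protocol. Two sites could also differ on whether a Week 27 dose needs a troponin result at all. What is at stake is subject safety and uniform conduct. No sample size, error rate or ORR analysis is affected.

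**Working it through.** The plan states no count of tested doses, so there is no figure to reproduce. The first two steps set passages side by side; the third is a count.

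**1. Raised value on treatment.** Both sections agree on the first actions (hold, repeat, evaluate). The question is what follows.

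| Troponin after evaluation | Section 4.3.3, C5 troponin item | Section 4.3.5, C5 troponin exception |
|---|---|---|
| Returns to normal | Investigator decides | BMS-986016 may resume; nivolumab not named |
| Stays raised | Investigator decides | Condition not met |

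The first row is compatible, apart from the silence on nivolumab. The second row is not: one section leaves treatment open and the other withholds its condition for resuming. The cross-reference from 4.3.3 to 4.3.5 does not settle the matter, because 4.3.3 then states a different rule of its own. Time also counts: 4.3.5 makes a delay of more than 6 weeks from the last dose a permanent stop, subject to the exceptions in 4.3.6.

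For nivolumab, 4.3.3 holds it, but the troponin exception does not say when it may restart. Whether the general rule in 4.3.5 then applies to nivolumab alone is not stated.

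**2. Subject admitted above ULN.** The entry route covers a 24-hour repeat above 1x ULN. The on-treatment hold starts at 1x ULN. A subject who enters by that route and whose value persists meets the hold at the next test. The general rule in 4.3.5 would accept a return to baseline, but troponin is listed among its exceptions with a return to normal instead. So it is unclear whether the baseline route is open to this subject.

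**3. Doses without a troponin result.** Inputs: dosing on "Day 1, Week 3, 5, 7, 9 and every other week thereafter" after Week 1 (Table 4.3-5), and the laboratory frequency in Table 5.1-5.

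- Doses through Week 23: (23 − 1)/2 + 1 = 12, all tested on either reading.
- Doses from Week 25 to Week H: (H − 25)/2 + 1.
- Reading A, troponin follows the laboratory frequency: every second dose from Week 25 is untested.
- Reading B, troponin is needed before every dose: none is untested.

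| Last dose counted | Doses from Week 25 | Untested, A | Share of all doses, A | Untested, B |
|---|---|---|---|---|
| Week 51 | (51 − 25)/2 + 1 = 14 | 7 | 7/26 = 27% | 0 |
| Week 103 | (103 − 25)/2 + 1 = 40 | 20 | 20/52 = 38% | 0 |
| Week 155 | (155 − 25)/2 + 1 = 66 | 33 | 33/78 = 42% | 0 |

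The counts are the same whether Week 25 or Week 27 is the first tested dose. The horizons are illustrative. Week 103 is about 24 months, the minimum in Section 3.1.4.1 before the optional stop for maximum clinical benefit.

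**The case against.** The strongest reply on timing is that there is no contradiction. The alternate-dose sentence introduces the general panel. Troponin has its own paragraph, its own collection window and its own review rule, under a column whose default is every dosing visit. On that reading no dose goes untested. On the other reading, the review sentence applies only to doses with a sample due, and again nothing conflicts. This stands in part: the text is ambiguous, and a reader who infers that the protocol definitely halves troponin testing goes beyond it. It does not remove the problem, because Section 3.1.4.6 groups troponin with the laboratory tests and defers to the table, while the table heading yields to its notes.

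On the raised value, the reply is that 4.3.3 points to 4.3.5, that 4.3.5 is permissive, and that investigator discretion can work alongside it. This stands when troponin normalises. It fails when troponin stays raised, since a discretion with no normalisation condition and a resume criterion that has one are not the same rule.

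On entry, a reader might infer that a subject admitted above ULN can never resume. The documents do not say that the elevation persists. Entry by this route also requires discussion with the Medical Monitor, and the C5 hold list is headed as drug-related events. The gap is conditional on persistence.

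The risk context also has limits. Section 1.1.5 places the fatal myocarditis at 240 mg BMS-986016, a dose it says C5 will not use. Troponin is one of six measures and the pre-dose ECG continues, so the documents do not support calling it the main early warning. The rule in 4.3.6 that stops both C5 drugs together concerns permanent discontinuation, so it is not evidence about resuming after a delay.

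**Conclusion.** The point holds in a bounded form. For a troponin that stays raised after cardiac evaluation, Sections 4.3.3 and 4.3.5 give different conditions for further treatment, and 4.3.5 does not say what applies to nivolumab although both drugs are held. If the elevation of a subject admitted above ULN persists, the hold applies with no clear route to resume. For timing, Tables 5.1-5 and 5.1-12 leave two readings open: 0% or 50% of doses from Week 25 without a troponin result, which is 0 or 20 of 40 by Week 103.

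The count assumes dosing every 2 weeks without delays and a subject still on treatment; one who stops earlier contributes fewer doses. Cited experience at the C5 dose is small: 4 subjects in Section 1.1.5, with 7.9 to 12.7 weeks of therapy, and 6 subjects in Section 1.4.3.3. The durations given for the four end before Week 23, so they do not inform the later period.

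A reader might also infer damage to the C5 cardiac safety analysis. The documents do not support a statement of its size: Section 8.4.3 is descriptive and does not name troponin among the laboratory parameters to be summarised. The reason to act is clear instruction on a safety test.

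**What to change.** The sponsor should reconcile Sections 3.1.4.6, 3.3.1 (criterion 2(i)viii), 4.3.3 and 4.3.5 and Tables 5.1-5 and 5.1-12 so that:

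- one troponin frequency after Week 23 is stated explicitly, in the same terms in both tables and in Section 3.1.4.6, and is consistent with the review-before-dose sentence;
- one passage states what permits further dosing after a raised troponin, including when it stays raised, and names the drug or drugs it covers, with the other passage referring to it;
- the handling of a subject admitted, or re-initiated, with troponin above ULN is consistent with the hold and resume rules.

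No view is taken on which frequency or which resume rule is right; that is for the sponsor and its clinical advisers.

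The cost is wording in two tables and up to four sections, with the ethics review that Section 9.1.1 requires for an amendment. If the sponsor confirms the alternate-dose reading, no test is added. If it confirms the every-dose reading, the most that is added is one local assay at each dose not otherwise tested, at visits that already take place.
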